### **3.6.2 Blinding**

Assessments regarding clinical recovery will be conducted by an assessor who is aware of the allocation of the patients in the study. The assessor will have a template in which to follow in order to ensure that the only difference between the two groups will be to ensure that the educational arm is able to open the pdf. Those who work in the clinic will not know

the allocation of the patient in the study but we are aware that this may be discovered during clinic visits. This will be a variable to consider when we analyze the data. An employee outside the research team will feed data into the computer in separate datasheets so that the researchers can analyze data without having access to information about the allocation

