### 3.4 Trial Design

This study is a blinded randomized control trial, which is the optimal trial design to determine whether a cause-effect relationship exists between our educational intervention and the current standard of care.

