### **3.5.2.5 Concomitant Care**

All patients will be seen in a tertiary level clinic. Clinicians are blinded to the allocation of the study participants. Therefore, regardless of their study allotment they will receive the current standard of care provided in the clinic.

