### **3.5.3 Outcomes**

#### **3.5.4 Primary Outcome Measures**

Targeted education provided to patients suffering from post-traumatic headache will be assessed using the RPQ. The RPCSQ is a 16-question instrument that examines post-concussion symptoms rated by the patient according to the increase in their frequency compared with premorbid levels. The total score is calculated based on 2 domains (cognitive and emotional-somatic) and ranges from 0 to 72. The RPQ has been shown to measure severity of postconcussion symptoms reliably with good test-retest and inter-rater reliability for individual symptom scores. Based on previous studies, splitting the RPQ into two subscale scores: RPQ-3 uses the sum of scores from three items (headaches, dizziness and nausea) and RPQ-13 uses the sum of scores of the other 13 items. Higher scores especially for the RPQ-13 subscale are associated with greater impact on lifestyle. For our study significance will be observed if patients reported symptoms decreased by 3 on the RPQ-3 and 10 on the RPQ-13.

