### **3.7 Methods: Data collection, management and analysis**

#### **3.7.1 Data Collection**

For all visits each patient will fill out a questionnaire (See Appendices for full surveys) using RedCap. If a patient is unable to enter the data using email directly, one of our research assistants will enter the data into the RedCap system via telephone interview. For the follow up survey if there is no response, we will attempt to contact the patient by phone three times. In regard to those patients seen in follow up in the clinic, we will ensure that they finish their follow up questionnaires after being seen by a healthcare professional to avoid unblinding. Patients' receiving the standard of care will be asked the same questions at week 0 and 12 with the same surveys as the education intervention arm of the study. A secure password protected master linking log will be able to house the patient name with study identification number.

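### The design section calls the trial blinded without qualification, although the recovery assessor knows the allocation and the masking of whoever takes telephone survey answers is not stated

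*Protocol*

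**What the plan says.** Section 3.4 (Trial Design) states: "This study is a blinded randomized control trial". It names no role.

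Section 3.6.2 (Blinding) then says: "Assessments regarding clinical recovery will be conducted by an assessor who is aware of the allocation of the patients in the study". The assessor works from a template intended to ensure that "the only difference between the two groups will be to ensure that the educational arm is able to open the pdf". The same section says clinic staff will not be told the allocation, and concedes that they may find out during visits. It also says: "An employee outside the research team will feed data into the computer in separate datasheets", so that the researchers can analyse without knowing the arms. Section 3.5.2.5 (Concomitant Care) adds: "Clinicians are blinded to the allocation of the study participants".

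On collecting the outcome, section 3.5.4 describes RPQ symptoms as "rated by the patient according to the increase in their frequency compared with premorbid levels". Section 3.7.1 (Data Collection) sets the default: "For all visits each patient will fill out a questionnaire", using REDCap. Its fallback, for a patient who cannot enter the data, is that "one of our research assistants will enter the data into the RedCap system via telephone interview".

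Section 3.5.2.2 puts the final RPQ, PART-O and QOLIBRI in the list of tasks for the contact that follows the third session. The purpose of that contact in the education arm is to check that the presentation could be opened. The same list gives the uploading of survey data to a student or research assistant who does not know the assignment. It also bars the caller from teaching and from discussing treatment or symptoms. Section 3.8.1 (Ethics) describes later questionnaires only as in person or by telephone interview and does not mention self-completion.

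**The concern.** The RPQ is subjective. If the person reading out its questions knows the arm, or has just confirmed that the patient opened the teaching file, tone, prompting or the patient's wish to please can shift answers in one arm and not in the other. PART-O and QOLIBRI are taken at the same contact and share the exposure.

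Participants will know whether they received education, so some reporting bias is unavoidable. The interviewer's contribution is avoidable, and the protocol as written neither prevents it nor says whether it occurs. The bare label in section 3.4 also invites readers of the results to assume more masking than the trial has.

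**Working it through.** The plan gives no figure to reproduce. The check sets the statements on each role side by side.

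| Role | Masking stated | Protocol section |
|---|---|---|
| Trial as a whole | blinded, no limit | 3.4 |
| Clinicians | masked | 3.5.2.5 |
| Clinic staff | masked as far as possible | 3.6.2 |
| Uploader of survey data | masked | 3.5.2.2 |
| Analysing researchers | masked | 3.6.2 |
| Assessor of clinical recovery | not masked | 3.6.2 |
| Research assistant taking telephone answers | not stated | 3.7.1 |
| Person doing the exit interview | not stated | 3.5.2.1 |
| Participants | not stated; will know if they were taught | 3.5.2.1, 3.5.2.2 |

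**Could the telephone interviewer know the arm?** The text leaves this open.

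- The masked role in 3.5.2.2 is defined by uploading, which is not the same as interviewing.
- Research assistants also handle the randomization envelopes (3.6.1). For patients identified in the emergency room, a research assistant is responsible for follow-up and for supplying the study materials (3.5.2.2).
- A person in either position could be the one on the telephone under 3.7.1.
- Section 3.7.1 orders the clinic questionnaires so as to protect blinding. It gives no matching protection for telephone completion.

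**How many final surveys could the shared contact affect?**

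- Inputs from 3.5.6: 35 enrolled per arm, 20% attrition.
- Expected completers per arm: 35 × (1 − 0.20) = 28.
- Control arm: there is no file to check, so this route affects 0.
- Education arm: 28 × p, where p is the share completed by telephone. The protocol does not give p. Taking p as an assumption:

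| p | Surveys affected (28 × p) |
|---|---|
| 0 | 0 |
| 0.25 | 7 |
| 0.50 | 14 |
| 1 | 28 |

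If self-completion works as the default, p is close to 0. If section 3.8.1 describes actual practice, a sizeable p cannot be excluded. These are counts of exposed surveys and say nothing about how far any answer would move.

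**The case against.** The strongest reply is that the protocol is candid. It has a section on blinding, names several masked roles, and openly discloses that the assessor knows the allocation. A one-line design statement is naturally read together with that section. There are also two safeguards: the template that limits what differs between arms, and the rule against teaching or discussing treatment or symptoms at the follow-up contacts. The RPQ is rated by the patient and self-entered by default.

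Most of this stands and sets the limits of the point. The safeguards reduce the risk but do not remove it. A script does not hide the arm from someone who has just asked whether the file opened, and a bar on discussion does not mask the person reading out the questionnaire.

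Three stronger readings are tempting, and the documents do not support them.

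- **That the protocol never says who is blinded.** This is true of section 3.4 alone; sections 3.5.2.2, 3.5.2.5 and 3.6.2 name masked roles.
- **That the aware assessor collects the primary outcome.** Section 3.6.2 speaks of clinical recovery and does not mention the RPQ. The shared file check makes the link plausible, but it remains an inference.
- **That the accounts of data handling contradict one another.** Telephone entry, upload and feeding separate datasheets may be successive steps by different people. The fault is that their relation is not stated.

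**Conclusion.** The point holds as a clarification with one useful change in conduct, and it should be fixed. The label in 3.4 does not fit an assessor who knows the allocation. The masking of the telephone interviewer is left open, and the education arm's final surveys share a contact with a task that reveals the arm.

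The shared-contact route reaches between 0 and about 28 education-arm surveys, and near 0 if self-completion works. That range rests on the plan's own attrition figure and on an unknown telephone share. A reader might infer that the primary comparison is biased or its error rate inflated. The protocol gives no basis for a size, a direction or a false-positive rate, and none is claimed. Confidence is medium, because the text permits the problem without showing that it happens.

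**What to change.** 1. **Collection (3.7.1, 3.5.2.2, 3.8.1).** Keep REDCap self-completion as the default and align 3.8.1 with it. Have any telephone completion, in both arms, done by a person unaware of allocation. This extends the role in 3.5.2.2 from uploading to interviewing; it should not be the assistant who opened that patient's envelope or supplied the materials. Do the file check and the exit interview only after the survey is submitted. State how telephone entry, upload and the separate datasheets relate.
2. **Label (3.4, 3.6.2).** Replace the bare term with a list of who is masked (clinicians, clinic staff as far as possible, uploader, analysing researchers) and who is not (participants, the recovery assessor). Say in 3.6.2 whether that assessor takes any RPQ answers. Where follow-up is already complete, record who took the answers so that the report can say so.

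**Cost.** Mostly wording and the order of calls. The education arm gains one short extra contact. The third-session file check falls after the final survey, so the outcome may be recorded before anyone confirms that the last presentation could be opened. One staff member must be kept unaware of allocation. Patients may still reveal their arm to the caller, and bias from participants knowing their own arm remains.

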**3.5.2.2 Summary of education by session: PowerPoint slides will be split into three distinct sections.**

*Initial session: (0 weeks): (In person)* We will outline the study. Approximately 30 minutes in duration.

[figure not shown]
- Review inclusion/exclusion criteria
- Explain study goals
- Obtain written/verbal informed consent
- We will cover topics such as defining the basic anatomy and the consequences of head trauma. We will include common symptoms along with when to seek medical guidance, medications to avoid and helpful lifestyle and treatment tips. Patients will be provided with links to approved websites.
- Prior to this session
  - Complete demographic information, medical history, trauma history and participant contact information (email or phone) will be gathered. If patients are identified in the ER, this information will be provided by the Triage nurse and forwarded to the research assistant who will be responsible for follow-up and providing the study materials.
  - Rivermead Post-Concussive Questionnaire (RPCSQ), PART-O and QOLIBRI (Yellow form: See Appendix) will be completed.
- *Second Session (6 weeks): (via email)*. Explain importance of keeping brain active; define the assessment of brain activity. 10-20 minutes to review the PowerPoint. Follow up will be done 1 week later either in person, email or via telephone to ensure patients are able to open the PowerPoint and have reviewed the literature. There will be no education or discussion about current treatment regimen or symptoms. Should a patient have questions regarding their current treatment plan or symptoms, our volunteers will put patients in contact with the Head Injury Nurse. All calls will be made during clinic hours in order to help facilitate communication with the clinic.

*Third Session (12 weeks)- (In person or sent via email)* We will explain importance of stress, sleep, and exercise on brain function, define the influence of lifestyle on recovery.

Approximate duration is 10-20 minutes. 1 week later follow up via telephone or email will occur by the methods listed above to ensure that the patient was able to open the PowerPoint. At this time we will:

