- Re-verify inclusion criteria to be done by Research Assistant. There will be no education or discussion about current treatment regimen or symptoms. Should a patient have questions regarding their current treatment plan or symptoms all calls will be made when the Head Injury Nurse is available to connect with patients directly.

- Rivermead Post-Concussive Questionnaire (RPCSQ), PART-O and QUOLIBRI will be completed via telephone or email and entered via REDCap into our database. Survey data will be uploaded by student or research assistant that is unaware of the patient's randomization.
- The patients who did not participate in the education seminar will fill out surveys at week 0 and 12.

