### **3.8 Ethics and dissemination**

#### **3.8.1 Ethics**

If the patient is interested in this study, they will receive the consent form explaining the purpose, procedure and requirements of the project from trained research assistants who will be available to answer questions regarding the project. Informed consent will be obtained from patients who will meet the eligibility criteria and agree to participate.

If the participant cannot sign and date the consent form properly they will be asked to provide consent with an "X", their initials or by signing with their alternate hand. If the participant is completely unable to provide written consent they will be asked for verbal consent and research staff obtaining consent will document the discussion on the consent form. Initial information will be extracted from the medical record including age, medical history, imaging results, Glasgow coma scale and neurological examination. Patients who agreed to participate will be asked to complete a demographic questionnaire, the Rivermead Post Concussion Symptom Questionnaire, the QUOLIBRI and the PART-O in person for the first session and then either again in person or by telephone interview.

Participant involved in the educational arm of the study must have email and easy access to a computer. When they are randomized they will be asked for their email address.

Participants will be given their study ID number when they consent. They will be asked to use this number as their ID on the survey. Follow up at 7 weeks will occur with the education arm 1 week after they have been emailed the power point material.

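### The education arm's final surveys are listed under its slide-check contact, and follow-up timing and mode are stated inconsistently, so differential prompting, timing and mode are not prevented

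*Protocol*

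**What the plan says.** **Education arm.** Section 3.5.2.2 describes the third session at 12 weeks and then a further contact about the slides: "1 week later follow up via telephone or email will occur by the methods listed above to ensure that the patient was able to open". Its stated purpose leads directly into a task list: "to ensure that the patient was able to open the PowerPoint. At this time we will". The list includes the RPQ, PART-O and QOLIBRI, which "will be completed via telephone or email and entered via REDCap into our database". Section 3.5.2.1 instead places survey completion, with an exit interview, at 12 weeks after enrolment.

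**Control arm.** Sections 3.5.2.2 and 3.7.1 have controls complete surveys at weeks 0 and 12. Section 3.7.1 adds that the questions and surveys are the same as in the education arm.

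**Assessor.** Section 3.6.2 states: "Assessments regarding clinical recovery will be conducted by an assessor who is aware of the allocation of the patients in the study". That assessor follows a template under which "the only difference between the two groups will be to ensure that the educational arm is able to open the pdf".

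**Mode of follow-up.** Section 3.7.1 says "For all visits each patient will fill out a questionnaire (See Appendices for full surveys) using RedCap". It then gives a fallback by telephone interview: "If a patient is unable to enter the data using email directly, one of our research assistants will enter the data". Three telephone attempts follow non-response. Section 3.8.1 says the instruments are completed "in person for the first session and then either again in person or by telephone interview", and does not mention email or self-entry.

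**The concern.** Every outcome in this trial is reported by the patient: the RPQ (sections 3.5.4 and 3.7.3), and the QOLIBRI, the PART-O and recalled use of health services (section 3.7.4). Such answers can shift with who asks, by what route, when, and what else is said at the same contact. As written, the contact that collects the final answers in the education arm may also ask about the educational material, and the person making it may know the allocation. Controls get no such question. If that contact shifts the ratings in one arm, the shift is part of the arm difference and cannot be separated from a true effect afterwards. An analysis plan cannot repair this once the data are collected, so the protocol has to settle it.

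**Working it through.** The point concerns procedure, and the protocol gives no figure for it. The check sets the statements side by side.

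1. **When are the final surveys taken?**
   - Education arm, section 3.5.2.2: session at week 12 plus one week, so 12 + 1 = week 13.
   - Education arm, section 3.5.2.1: week 12.
   - Controls, sections 3.5.2.2 and 3.7.1: week 12.
   - Result: the arms either match or differ by one week, depending on which section staff follow.

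2. **What else happens at that contact?**
   - Education arm: the slide check (3.5.2.2), also written into the assessor's template (3.6.2). The exit interview appears only in the description of the educational intervention (3.5.2.1).
   - Controls: the same template without the slide check.
   - Order of slide check and survey: not stated. Whether the reminder comes before the ratings is left to the person making the contact.

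3. **By what route?**
   - Section 3.5.2.2: telephone or email.
   - Section 3.7.1: self-entry in REDCap, telephone interview if the patient cannot use email, and three calls after non-response. Clinic attenders finish their questionnaires after being seen.
   - Section 3.8.1: in person or telephone interview.
   - Result: the first two can be read together. The third leaves out the route that 3.7.1 makes the default. None assigns a route by arm.

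4. **Who knows the allocation?**
   - The assessor does (3.6.2). The person who uploads the survey data does not (3.5.2.2), and section 3.4 calls the trial blinded. Blind upload protects later handling of the data, not the answer as it is given.

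5. **Scale, as an illustration only.** Inputs: 28 evaluable patients per arm (section 3.5.6, where 28 / 0.8 = 35 are enrolled), two-sided alpha 0.05 (3.5.6; threshold repeated in 3.7.7), no true effect, and an assumed shift b in reporting between the arms, in SD units. The standard error of the difference is √(2/28) = 0.267 SD. The probability of a significant result is 1 − Φ(1.96 − b/0.267) + Φ(−1.96 − b/0.267). For b = 0.2 this is 1 − Φ(1.21) + Φ(−2.71) = 0.116.

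| Assumed shift (SD) | Two-sided error |
|---|---|
| 0 | 5.0% |
| 0.1 | 6.6% |
| 0.2 | 11.6% |
| 0.3 | 20.2% |
| 0.5 | 46.5% |

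The table shows how sensitive a trial of this size is to a reporting shift in either direction. It does not estimate the shift here, for which the protocol offers no basis.

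**The case against.** The strongest reply is that the protocol tries to keep the arms alike. Section 3.7.1 covers every patient and promises the same questions and surveys. The template in section 3.6.2 is a standardising device, and it implies that the assessor uses it with controls too. The slide-check contact may itself be by email, and section 3.5.2.2 bars education or discussion of treatment or symptoms at it. The task list there also contains a line on controls, so it is not purely a script for the education contact. Finally, education patients have attended a session and received slides, so they know their arm already, and a question about opening a file may add little.

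Much of this stands. A reader might infer that education patients are more likely to be interviewed while controls self-complete by email, and might then put a number of RPQ points on the resulting artefact. The protocol does not support that. No section sets mode by arm, and neither the interview rates nor any mode effect can be derived from it. If both arms follow 3.7.1 alike, the difference due to mode is zero. Even the direction is open: section 3.8.1 stresses email and computer access for the education arm, which could move controls towards the telephone instead.

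The reply does not remove the gap. Identical questions do not fix the timing, the route, the order or the other content of the contact. Moving the slide check will not hide the allocation from patients, but it does remove an avoidable cue from outcome collection.

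**Conclusion.** The point holds as a weakness in procedure. The education arm's final surveys are listed under an arm-specific contact, that arm's timing is given as both week 12 and one week later, and follow-up mode is not stated consistently. An assessor who knows the allocation carries the slide check in the assessment template for one arm only. Differential prompting, timing and mode are thus possible and not prevented. Their size and direction are unknown, and no estimate in RPQ points is justified.

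The conclusion rests on reading the list in section 3.5.2.2 as the tasks of the contact that introduces it. If section 3.5.2.1 governs, the one-week difference disappears, but the arm-specific template item and the conflict over mode remain. That prompting comes before the ratings is a risk, not something the protocol states. The correction is worth making because it is cheap and all outcomes are patient-reported.

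**What to change.** State one follow-up procedure for both arms:

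- A REDCap link for self-completion, sent on the same study day (week 12) in each arm.
- Telephone only after non-response, using the three attempts already in section 3.7.1, or when the patient cannot use email.
- The slide check taken out of the assessment template and done by email or telephone only after the surveys have been submitted.
- Sections 3.5.2.1, 3.5.2.2, 3.6.2, 3.7.1 and 3.8.1 made to agree on day, route and content of the contact, including whether clinic attenders still complete the questionnaires there.

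The link and the telephone fallback already exist, so most of this is rewording. The added work is a short separate slide-check message to about 35 education patients.
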